As it is yet unclear whether cancer survivors would benefit most from aerobic or strength training, this study will be the first step toward designing an intervention to test whether one exercise modality has superiority over another among cancer survivors. Thus, an adaptive intervention is an ideal design to determine which type of intervention is optimal. We propose to employ an intervention in which participants who are not responding to an exercise modality are re-assigned to a combined modality, thus tailoring the exercise intervention to respond to the needs of participants.

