### **3.0 STUDY AIMS**

1. Determine the feasibility of an individually-adaptive exercise intervention among breast cancer survivors with reduced cardiorespiratory fitness through examination of recruitment rate, enrollment rate, loss to follow-up, intervention adherence, and relative dose intensity (ratio of total completed to total planned cumulative dose)

2. Examine the endpoint of (a) safety; and explore the endpoints of (b) cardiorespiratory fitness; (c) functional capacity; (d) physiologic changes; and (e) patient reported outcomes (PRO) in the intervention vs control arms.
3. Examine the endpoint of (a) safety; and explore the endpoints of (b) cardiorespiratory fitness; (c) functional capacity; (d) physiologic changes; and (e) patient reported outcomes (PRO) in the AE vs RE vs AE+RE intervention arms.

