## 4.0 STUDY DESIGN

### 4.1 Description of Study

This is a pilot study of a 2-arm randomized trial with a 2:1 initial allocation to exercise intervention or waitlist control (see Appendix B for study schema). The intervention group will then be randomly assigned (1:1) to receive either a 12-week aerobic exercise (AE) intervention or a 12-week resistance exercise (RE) intervention.

At 12 weeks, the intervention group will be assessed for intervention response, defined as a  $\geq 5\%$  increase in 6-minute walk distance (6MWD) over baseline. Non-responders to either AE or RE will receive 12 weeks of combined AE+RE. Intervention responders will continue the exercise intervention in their current assignment, either AE or RE alone, for the additional 12 weeks.

This study will employ a waitlist control. After 24 weeks, the waitlist control group will receive a digital copy of sessions provided to the intervention arm. The control and intervention arms' schedule of evaluations will be identical across all 24 weeks of the trial.

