#### 4.3.4 Randomization

Participants will be randomly allocated to the intervention or waitlist control arm using blocked randomization (2:1 intervention to control), stratified upon whether the participant has received “AC” chemotherapy (doxorubicin and cyclophosphamide combination therapy). Intervention participants will then be randomized to either aerobic exercise training or resistance strength training, again using blocked randomization stratified on AC treatment history. Randomization will be performed in REDCap with the REDCap Randomization module.

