Next, the analysis will explore the impact of the intervention on the outcome of CRF in intervention participants versus waitlist control participants using generalized linear models (GLM) comparing baseline to 24-week measurements. This analysis will be repeated for the additional outcomes of functional capacity, i.e., submaximal exercise capacity; physiologic changes, i.e., thigh IMF:SM, abdominal depots of fat (VAT, SQ, RP, and IP fat), and body weight; and patient reported outcomes, i.e., QOL, perceived well-being, and fatigue. These analyses will be performed according to the intent-to-treat principle, where outcomes are analyzed by intervention assigned, regardless of the level of adherence. A secondary per protocol analysis will be conducted, and these results will be reported and interpreted together with the intent-to-treat analysis. This per protocol analysis will include only those participants who (a) completed all clinic visits and who completed at least 85% of the required physical activity. In addition, this secondary analysis will investigate factors related to a lack of intervention adherence, which will include baseline measures of perceived well-being, mood disturbance, perceptions of PA, fatigue, and insomnia.

For objective 3, the analysis will explore the impact of AE vs RE vs combined AE+RE on safety outcomes using generalized linear models (GLM) comparing pre-intervention measurements to post-intervention measurements. Next, this analysis will be repeated for the additional outcomes of CRF, functional capacity, physiologic changes, and patient reported outcomes of QOL, perceived well-being, and fatigue.

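### Objective 3 compares AE, RE and AE+RE as arms, but AE+RE holds only Week-12 non-responders, so its contrast with continued AE or RE is confounded with response

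*Combined protocol and SAP*

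**What the plan says.** The only randomisation inside the intervention group is the first one. Section 4.3.4 (Randomization) states: "Intervention participants will then be randomized to either aerobic exercise training or resistance strength training". Section 4.1 defines response at Week 12 as a 6MWD gain of at least 5% over baseline and then applies a rule. "Non-responders to either AE or RE will receive 12 weeks of combined AE+RE", while "Intervention responders will continue the exercise intervention in their current assignment, either AE or RE alone". Section 2.2 says the same: "participants who are not responding to an exercise modality are re-assigned to a combined modality". No other route into AE+RE is described.

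Aim 3 in Section 3.0 nevertheless treats the three regimens as arms, ending with "patient reported outcomes (PRO) in the AE vs RE vs AE+RE intervention arms". In Section 10.0, Objective 3 follows suit: "the analysis will explore the impact of AE vs RE vs combined AE+RE on safety outcomes", by generalized linear models "comparing pre-intervention measurements to post-intervention measurements". The same analysis is then repeated for cardiorespiratory fitness, functional capacity, physiologic changes and patient-reported outcomes.

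Section 10.0 also has an intent-to-treat sentence that classifies participants by allocation whatever their adherence. It stands in the Objective 2 paragraph. Section 4.3.5 schedules CPET and MRI at baseline and Week 24 only, and the walk test at all three visits.

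**The concern.** Membership of AE+RE is fixed by the Week-12 walk result. No percent gain occurs both in someone on AE+RE and in someone who stayed on a single modality. For functional capacity, the variable that sorted the groups is also an outcome on which they are compared.

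Three things are left undefined:

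- **Who AE and RE are.** If they mean first assignment, AE+RE overlaps both. If they mean those who stayed, both groups are responders only, and AE versus RE also loses its randomised basis.
- **How intent-to-treat applies.** Carried over to Objective 3, the sentence in the Objective 2 paragraph gives two groups, not three.
- **What pre-intervention means for AE+RE.** From baseline, the change includes 12 weeks of single-modality training. A Week-12 starting point does not exist for CPET or MRI.

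Safety, a secondary endpoint, has an exposure problem as well. Someone who stays has up to 24 weeks on one modality, against at most 12 on AE+RE.

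Section 10.0 says the exploratory results will inform a larger intervention, and Section 2.2 says that "an adaptive intervention is an ideal design to determine which type of intervention is optimal". An artefact of the Week-12 rule could therefore be carried into the next trial as evidence about modality.

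**Working it through.** The documents give no effect size, SD, response rate or error rate for Objective 3, so there is no figure of theirs to reproduce.

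**Inputs from the documents.** There are 30 participants (Section 4.3.1), allocated 2:1 and then 1:1 (Section 4.1). That gives 30 × 2/3 = 20 intervention participants, 10 starting on AE and 10 on RE.

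**Assumed inputs.** Response rate p is 30-70%. The correlation rho between an outcome's improvement to Week 24 and the Week-12 6MWD gain is 0 to 0.7. Walk-test error SD is 15, 25 or 35 m. Between-person SD of true 6MWD is 0 to 80 m, around a mean of 450 m. The null is that AE+RE and continuing on one modality have the same true effect.

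**1. Group size.** The expected AE+RE group is 20(1 − p): 14, 10 or 6 people at p = 30, 50 or 70%.

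**2. Bias on a general outcome, scored so that higher is better.** Under bivariate normality the gap (stayers minus AE+RE) is rho × phi(z) / [p(1 − p)] SD of change, where phi is the standard normal density at the cut-off z.

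- p = 50%: phi = 0.399, and 0.399/0.25 = 1.60.
- p = 30% or 70%: phi = 0.348, and 0.348/0.21 = 1.66.
- Multiplying by rho gives 0 at rho 0, 0.48-0.50 at 0.3, 0.80-0.83 at 0.5 and 1.12-1.16 at 0.7.

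In simulated trials of 20, a t-test at an assumed two-sided 5% level rejected this true null in 15-18%, 39-43% and 73-79% of runs at rho 0.3, 0.5 and 0.7. Grouping the same data by first assignment gave a mean bias of about 0 and rejection in 4.5-5.3%.

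**3. Bias on 6MWD.** The model is Y0 = T + e0, Y12 = T + g + e12 and Y24 = T + g + e24, with the same gain g for everyone. A responder has Y12 ≥ 1.05 × Y0.

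| Test-error SD | 15 m | 25 m | 35 m |
|---|---|---|---|
| Raw gap, baseline to Week 24, p 30-70% | 17-18 m | 29-30 m | 40-42 m |
| Gap adjusted for baseline 6MWD, between-person SD 0 (p = 50%) | 0 m | 0 m | 0 m |
| Same, between-person SD 20 m | 12 m | 14 m | 13 m |
| Same, between-person SD 50 m | 16 m | 24 m | 30 m |
| Same, between-person SD 80 m | 17 m | 27 m | 35 m |

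Adjusting for both baseline and Week-12 6MWD brings the gap to zero in this linear model, but only by extending a fitted line across the 5% cut-off. At n = 20 and between-person SD 50 m, the SD of that estimate is 15, 25 and 34 m, against 9, 15 and 21 m for the raw contrast.

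**4. Week 12 as the starting point.** With no true change in Weeks 12-24, AE+RE shows a spurious 6MWD gain of 5-12, 9-20 and 12-28 m at the three error SDs, because it was selected on low Week-12 values. Those who stay show a spurious fall over the same ranges. If Week 12 is used for both groups, the bias changes sign. If it is used for AE+RE alone, a 12-week change is set against a 24-week one.

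**5. Safety exposure.** With an equal weekly event rate, the chance of at least one event is 1 − exp(−rate × weeks).

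- At 0.02 per week: 38% over 24 weeks and 21% over 12.
- At 0.05 per week: 70% and 45%.

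The rates are illustrative, and no dropout is assumed.

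**6. What the randomised contrast offers.** The standard error of a 10 versus 10 difference is √(2/10) = 0.45 SD. The detectable difference at 80% power and an assumed two-sided 5% level is (1.96 + 0.84) × 0.447 = 1.25 SD.

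**The case against.** The strongest reply is proportion. This is a 30-person pilot, its primary endpoint is intervention discontinuation, and the aims and Section 10.0 describe these comparisons as exploratory. No test or error rate is set for Objective 3, and Section 10.0 makes exploration of the non-safety outcomes conditional on feasibility and safety. The sentence in Section 2.2 just before the one on the ideal design presents the study as a first step toward a later superiority test. All of this stands and limits the severity. It does not remove the problem: the bias comes from the assignment rule, and more participants would not reduce it.

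A second reply is that assignment follows a known cut-off on a measured variable. A reader might infer that the two groups are beyond any comparison. The documents do not support that: adjustment for baseline and Week-12 6MWD is possible in principle. What holds is that there is no overlap, so any such estimate rests on extrapolation and is very imprecise at this sample size.

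A third reply is that the intent-to-treat sentence already settles the grouping. It does not, because it cannot produce the three groups that Objective 3 names.

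A reader might also see a contradiction between the SMART label in Appendix A and the lack of randomisation at Week 12. The documents do not define the term and do describe two successive randomisations, so that is at most a matter of labelling.

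**Conclusion.** The concern holds and should be fixed. The structural part needs no assumptions: AE+RE is filled by a response rule, only AE versus RE is randomised, and the planned three-group model compares groups sorted on response.

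The size does rest on assumptions. It is about 0.5 to 1.2 SD for correlations of 0.3 to 0.7, and 17-42 m on 6MWD for test-error SDs of 15-35 m. After adjustment for baseline 6MWD, anything from about 0 to 35 m remains, depending on a between-person SD that the documents do not give.

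A reader might infer that AE+RE must look worse on every outcome, or that the trial's main conclusion is compromised. Neither follows. An outcome uncorrelated with Week-12 6MWD gain is not biased by the selection, and on 6MWD the direction reverses if change is counted from Week 12 in both groups. The primary endpoint is untouched. The affected outcomes are exploratory apart from safety, where per-person risk is not comparable because exposure differs.

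**What to change.** In Section 10.0 and Aim 3:

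- Make the Objective 3 comparison AE-first versus RE-first as randomised. Include all intervention participants whatever happens at Week 12, analyse at Week 24 and, where measured, at Week 12, and describe it as a comparison of starting strategies. State that the intent-to-treat sentence applies to it.
- Report AE+RE descriptively among non-responders, and define pre-intervention for that group. State that its 6MWD change from Week 12 is inflated by regression to the mean, and that any comparison with those who stay is confounded with response.
- Report adverse events by first assignment and, descriptively, per participant-week by modality in use. First reconcile Appendix A, which lists assessments at 12, 24, 36 and 48 weeks, with the 24-week schedule in Sections 4.3.4 (Data Collection) and 4.3.5.
- Stop calling AE+RE an arm.

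This changes the analysis text only. It needs no new data and leaves the exercise assignment as it is. The cost is the three-way comparison, and what remains is about 10 versus 10 and imprecise. The effect of adding the second modality would stay unanswered.

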#### 4.3 Study Procedures

#### 4.3.1 Recruitment

This project will recruit 30 study participants through a multi-pronged approach:

Seattle Cancer Care Alliance (SCCA) clinics: At SCCA, we will work with the breast oncology clinic research team to obtain a list of potentially eligible research participants that will include patient name, phone number, and mailing address. This eligibility will be based on age and approximate end date of chemotherapy or Herceptin therapy. Potentially eligible participants identified through SCCA will receive a mailed letter endorsed by their oncologist inviting them to call the study coordinator for more information and/or screening. The study team may follow up proactively with a phone call no less than two weeks after sending the letter.

Breast cancer support groups in the community: Study information will be provided to breast cancer support groups in the community by sharing study flyers (paper, electronic, or Web versions) with the organizers of these groups and by giving presentations at in-person group events, as permitted by organizers.

Re-contacting previous breast cancer research participants: The pool of previous breast cancer research participants will be generated from past projects under the purview of the study's principal investigators or shared from affiliate investigators. Previous participants or candidates will be contacted via phone, email, or mailed letter, depending on what information is available to the study PIs.

The UW ITHS Leaf tool: The University of Washington's Leaf system will be used to generate an identifiable cohort of potentially eligible patients in the UW Medicine system. The study will query the database for patients who meet key eligibility criteria and who have recently visited the UW Medicine system for treatment. Candidates generated from this list will be sent a letter that describes the study and invites them to contact the study team should they be interested in participation. The study team may follow up proactively with a phone call no less than two weeks after sending the letter.

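### Section 10 never analyses the three groups the trial randomises: Objective 2 pools the two exercise strategies, and Objective 3 drops the waitlist arm and adds a group formed by week-12 non-response

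*Combined protocol and SAP*

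**What the plan says.** Section 4.3.1 sets the size: "This project will recruit 30 study participants through a multi-pronged approach". Section 4.1 describes a randomised trial "with a 2:1 initial allocation to exercise intervention or waitlist control", and continues: "The intervention group will then be randomly assigned (1:1) to receive either a 12-week aerobic exercise (AE) intervention", or the resistance equivalent. The Randomization section (4.3.4) agrees: "Intervention participants will then be randomized to either aerobic exercise training or resistance strength training", with the same stratification at both steps.

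The combined regimen has a different origin. Under Section 4.1, response at week 12 means a gain of at least 5% in six-minute walk distance, and "Non-responders to either AE or RE will receive 12 weeks of combined AE+RE". Responders stay on their assigned modality. The waitlist arm has the same evaluations at the same times (Sections 4.1 and 4.3.5).

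Section 10 plans two sets of comparisons. Objective 2 looks at the "outcome of CRF in intervention participants versus waitlist control participants", then repeats this two-group analysis for the other outcomes, by intention to treat. In Objective 3, "the analysis will explore the impact of AE vs RE vs combined AE+RE on safety outcomes using generalized linear models (GLM", from before to after intervention, and this is repeated for fitness, functional capacity, physiologic and patient-reported outcomes. Aim 3 in Section 3.0 confines this comparison to the intervention arms. Section 10 attaches its intention-to-treat sentence to the Objective 2 analyses and does not say how women are assigned to the three Objective 3 groups.

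**The concern.** Two randomisation steps protect two questions: does each starting strategy do better than no program, and does one do better than the other. Section 10 asks neither in randomised form. Objective 2 merges the strategies. Objective 3 names a group that no one was randomised to and leaves out the only arm that shows what happens without exercise.

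At stake is what the exploratory results can tell the designers of the next trial. Section 10 wants these outcomes to inform the potential impact of a larger intervention. A pooled estimate cannot show whether both strategies contribute. A pre-to-post change within a modality also carries anything that changes in all women over 24 weeks, such as retest gain or recovery. Comparing regimens received sets women who had improved by week 12 against women who had not.

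**Working it through.** The plan states no effect size, SD, alpha or power, so there is no figure of its own to reproduce. What can be checked is which groups exist, what each planned contrast estimates, and how precise the missing contrasts would be.

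**1. Randomised groups.** Exercise: 30 × 2/3 = 20. Waitlist: 30 × 1/3 = 10. AE-first: 20 × 1/2 = 10. RE-first: 20 × 1/2 = 10.

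**2. What Objective 2 estimates.** Write d_AE and d_RE for the effects of starting with AE or RE, each against waitlist. With equal numbers the pooled contrast estimates P = (d_AE + d_RE)/2. Let one strategy have effect d and the other a fraction f of it:

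| f | P |
|---|---|
| 0 | 0.50 d |
| 0.5 | 0.75 d |
| 0.75 | 0.875 d |
| 1 | d |

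So for f between 0 and 1 the stronger strategy's effect is at most halved.

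**3. Could Objectives 2 and 3 together recover each effect?** If AE-first and RE-first were compared as randomised, giving D = d_AE − d_RE, then d_AE = P + D/2 and d_RE = P − D/2, and nothing would be lost. Objective 3 does not clearly provide D. Once AE+RE is a separate group made up of non-responders from both strategies, the women left in AE and RE are the responders. For illustration, with an assumed non-response of 25% in both strategies the groups are 7.5 AE, 7.5 RE and 5 AE+RE; at 50% they are 5, 5 and 10. Response is defined on six-minute walk distance, which is itself one of the functional capacity outcomes, so for that outcome the grouping depends on its own interim value.

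**4. Is the contrast planned elsewhere?** The per-protocol analysis, the moderator analyses (BMI, baseline activity, adherence) and the midpoint chi-square test in Appendix A do not compare either strategy with waitlist. Section 4.2.2 promises an adverse-event review for each study group but does not define the groups, and it covers safety only.

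**5. Precision if the randomised groups are modelled.** Assumptions: no dropout, equal SD, one three-group model with 30 − 3 = 27 residual df, t(0.975, 27) = 2.052. Half-width = t × SD × √(1/n1 + 1/n2).

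- One strategy vs waitlist, or AE-first vs RE-first (10 vs 10): 2.052 × √0.20 = 2.052 × 0.447 = 0.92 SD.
- Pooled vs waitlist (20 vs 10): 2.052 × √0.15 = 2.052 × 0.387 = 0.79 SD.

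If loss reached the plan's 40% feasibility limit evenly (6 per group), separate two-group comparisons would give half-widths of about 1.29 SD (6 vs 6) and 1.06 SD (12 vs 6).

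**The case against.** The analysis matches the stated aims. Aim 2 is exercise against control, Aim 3 compares regimens within the exercise group, and the trial is described as having two arms. The outcomes concerned are exploratory, are examined only if feasibility and safety look acceptable, and carry no power claim. All of this stands, and it limits the weight of the point. It does not explain why a comparison involving a response-defined group is planned while the randomised ones are not.

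Three stronger readings are tempting, and the documents do not support them.

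- *Pooling makes a single-strategy effect vanish.* It halves it in expectation when the other strategy has no effect, and reduces it less when both help. Full cancellation needs equal and opposite effects.
- *The trial will miss an effect that separate contrasts would find.* This depends on an assumed extreme. Non-responders receive the combined regimen before the week-24 outcomes, so the strategies probably converge in part. Take an assumed effect of 0.8 SD, 10 per group, two-sided 5% and no dropout. Simulated power, pooled against strategy-specific, is 14% vs 41% if the other strategy has no effect, 31% vs 40% at half the effect, 41% vs 41% at three quarters, and 51% vs 41% if both are equal. Two unadjusted contrasts also carry about a 9% chance of at least one false positive. Power is therefore not the argument.
- *The pilot is meant to select the modality for the next trial.* Section 2.2 does say that "an adaptive intervention is an ideal design to determine which type of intervention is optimal", but it also calls this study a first step towards a trial that would test superiority.

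**Conclusion.** The point holds as a gap in the exploratory analysis. Three groups of about 10 are randomised, and no planned analysis compares either strategy with waitlist or clearly compares AE-first with RE-first as randomised. The pooled contrast remains valid for the average effect and is the more precise one if both strategies work about equally, so it should stay.

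The confounding by response is conditional on Objective 3 groups being taken by regimen received. Section 10 does not say so, but a separate AE+RE group cannot be formed by assignment.

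The gain from the change is interpretable estimates, not power: half-widths of about 0.92 SD for each strategy against waitlist and 0.79 SD pooled, assuming 10 per group, a common SD and no dropout. The primary endpoint, intervention discontinuation, is not affected.

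**What to change.** In Section 10, for each exploratory outcome, fit one model with three groups as randomised: AE-first, RE-first and waitlist. Keep women who move to AE+RE in the group they were assigned to. From that model report, each with a 95% confidence interval and labelled exploratory:

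1. pooled intervention vs waitlist (Objective 2, unchanged);
2. AE-first vs waitlist;
3. RE-first vs waitlist;
4. AE-first vs RE-first.

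Tabulate adverse events for the same three groups. Describe outcomes by regimen received (AE, RE, AE+RE) separately, and state that this comparison is not randomised.

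The cost is wording and a few contrasts. No visits, measurements or participants are added. The downside is more estimates: Section 10 names about 11 outcomes for Objective 2, so items 2 and 3 add 2 × 11 = 22 estimates, with wide intervals and no multiplicity control. The text should say so.
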